15.4.2. Overdose

An overdose is any dose of study treatment administered to a subject or taken by a subject that exceeds the dose assigned to the subject according to the protocol. Overdoses are not considered AEs and should not be recorded as an AE on the CRF; however, all overdoses must be recorded on an Overdose form and faxed to Biogen or designee within 24 hours of the site becoming aware of the overdose. An overdose must be reported to Biogen or designee even if the overdose does not result in an AE. If an overdose results in an AE, the AE must be recorded. If an overdose results in an SAE, both the SAE and Overdose forms must be completed and faxed to Biogen or designee. All study treatment-related dosing information must be recorded on the dosing CRF.

15.4.3. Medical Emergency

In a medical emergency requiring immediate attention, study site staff will apply appropriate medical intervention, according to current standards of care. The Investigator (or designee) should contact the study's Medical Director. Refer to the Study Reference Guide's Official Study Contact List for complete contact information.

15.4.3.1. Unblinding for Medical Emergency

Not applicable.

CONFIDENTIAL

The information contained herein may not be used, disclosed, or published without the written consent of Biogen MA Inc.

15.5. Contraception Requirements

Subjects of childbearing potential must practice effective contraception (as determined by the Investigator) during the study and be willing and able to continue contraception for 30 days after their last dose of study treatment. In addition, male subjects should not donate sperm for the duration of the study and for at least 30 days after their last dose of study treatment.

For the purposes of this study, women who do not meet one of the following criteria listed below are considered to be physiologically capable of becoming pregnant and are, therefore, defined as women of childbearing potential:

- Postmenopausal
 - 12 months of natural (spontaneous) amenorrhea without an alternative medical cause and a serum follicle-stimulating hormone level >40 mIU/mL
 - 6 weeks after surgical bilateral oophorectomy with or without hysterectomy
- Posthysterectomy
- Female surgical sterilization (e.g., bilateral tubal ligation)

For the purposes of the study, highly effective contraception is defined as use of 1 or more of the following:

For females:

- Established use of oral, injected, or implanted hormonal methods of contraception.
- Placement of an intrauterine device or intrauterine system.
- Barrier methods of contraception with use of a spermicide: condom or occlusive cap (diaphragm or cervical/vault caps) with spermicidal foam/gel/film/cream suppository. The use of barrier contraceptives should always be supplemented with the use of a spermicide.
- Male surgical sterilization (with the appropriate postvasectomy documentation of the absence of sperm in the ejaculate). (For female subjects participating in the study, male sexual partners must have undergone surgical sterilization.)

For males:

- Effective male contraception includes a vasectomy with negative semen analysis at follow-up, or the use of condoms with spermicide.

True abstinence, when this is consistent with the preferred and usual lifestyle of the subject, can be considered an acceptable method of contraception based on the evaluation of the Investigator who should also take into consideration the duration of the clinical trial. Periodic abstinence (e.g., calendar, ovulation, symptothermal, postovulation methods) and withdrawal are not considered acceptable methods of contraception.

Pregnancy reporting is described in Section 15.4.1.

CONFIDENTIAL

15.6. Safety Responsibilities

15.6.1. The Investigator

The Investigator's responsibilities include the following:

- Monitor and record all AEs, including SAEs, regardless of the severity or relationship to study treatment.
- Determine the seriousness, relationship, and severity of each event.
- Determine the onset and resolution dates of each event.
- Monitor and record all pregnancies and follow up on the outcome of the pregnancy.
- Complete an SAE form for each SAE and fax it to Biogen or designee within 24 hours of the study site staff becoming aware of the event.
- Pursue SAE follow-up information actively and persistently. Follow-up information must be reported to Biogen or designee within 24 hours of the study site staff becoming aware of new information.
- Ensure all AE and SAE reports are supported by documentation in the subjects' medical records.
- Pursue AE follow-up information, if possible, until the event has resolved or has become stable.
- Report SAEs to local ethics committees, as required by local law.

15.6.2. Biogen

Biogen's responsibilities include the following:

- Before study site activation and subject enrollment, the Clinical Monitor (or designee) is responsible for reviewing with study site staff the definitions of AE and SAE, as well as the instructions for monitoring, recording, and reporting AEs and SAEs.
- Biogen is to notify all appropriate regulatory authorities, central ethics committees, and Investigators of SAEs, as required by local law, within required time frames.

CONFIDENTIAL

The information contained herein may not be used, disclosed, or published without the written consent of Biogen MA Inc.

16. STATISTICAL METHODS AND DETERMINATION OF SAMPLE SIZE

The objectives of the study and the endpoints to be analyzed are listed in Section [6](#).

16.1. Pharmacokinetics

Not applicable.

16.2. Pharmacodynamics

16.2.1. Analysis Population

The pharmacodynamic population is defined as all subjects who receive at least 1 dose of study treatment and have at least 1 pharmacodynamic measurement after Baseline.

16.2.2. Methods of Analysis

Statistical analyses will be [REDACTED] and descriptive in nature, with appropriate measures of precision provided where applicable. There is no planned statistical hypothesis testing in this study.

16.2.2.1. Analysis of the Primary Endpoint

Counts and change from Baseline in counts for each of the lymphocyte subsets will be descriptively summarized at each applicable visit. Furthermore, the primary endpoints will be summarized in various ALC subgroups to evaluate the nature of change in each subset in relation to the change in ALC. Additionally, a mixed model for repeated measures (MMRM) will be used, which will be fit with the change from Baseline for each of the lymphocyte subsets as the dependent variable and will include ALC subgroups, visit, corresponding Baseline counts, age, gender, and ALC groups-by-visit interaction as fixed effects to estimate the difference between ALC subgroups. Point estimates and 2-sided 90% confidence intervals (CIs) will be derived from the model. Appropriate transformation may be performed based on the distribution of data.

[figure not shown]
ALC subgroups of interest include (1) subjects who have all ALC values \geq LLN up to Week 48, (2) subjects who have at least 1 ALC value $<$ LLN over 48 weeks, and (3) subjects who have at least 2 ALC values $<$ LLN over 48 weeks. Additional subgroups will be further defined in the Statistical Analysis Plan.

16.2.2.2. Analysis of the Secondary Endpoints

For the secondary endpoints (IgG isotypes and ALCs), actual values and change from Baseline will be descriptively summarized at each applicable visit. In addition, the same type of MMRM used for analysis of primary endpoints will be employed, which will be fit with the change from Baseline in each of the IgG isotypes and ALCs as the dependent variable and will include visit, corresponding baseline value, age, and gender as fixed effects.

CONFIDENTIAL

The information contained herein may not be used, disclosed, or published without the written consent of
Biogen MA Inc.

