DMF was generally well tolerated and demonstrated an acceptable safety profile. The most common AEs associated with DMF were flushing and gastrointestinal (GI) events. In subjects who experienced these types of events, the events were generally mild or moderate in intensity, tended to decrease in incidence after the first month, and only infrequently led to treatment discontinuation. There are a number of potential management strategies for these side effects. In the Phase 2 and 3 controlled and uncontrolled clinical studies in subjects with RRMS, BG00012 treatment was associated with a gradual decrease from baseline in mean leukocyte counts driven primarily by decreases in mean lymphocyte counts; mean lymphocyte counts decreased by approximately 30% of their baseline value after 1 year and then plateaued and remained stable through more than 6 years of follow-up. While decreases in lymphocyte counts have been observed with BG00012 treatment, in the placebo controlled Phase 2 and 3 studies BG00012 was not associated with an increased risk of infection, serious infection, or opportunistic infection compared with placebo. However, in the long-term extension study (109MS303), progressive multifocal leukoencephalopathy (PML) has occurred in the setting of severe, prolonged lymphopenia following BG00012 administration. PML has also been reported in the postmarketing setting in the presence of prolonged moderate to severe lymphopenia. The majority of all cases occurred in patients with lymphocyte counts $<0.5 \times 10^9/L$. With open-label

CONFIDENTIAL

The information contained herein may not be used, disclosed, or published without the written consent of
Biogen MA Inc.

and marketed use of BG00012, there has been no other evidence of an increased risk of infections, serious infections, or opportunistic infections.

See the Investigator's Brochure for detailed information on clinical studies.

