16.7. Sample Size Considerations

The sample size for this study is not based on formal hypothesis testing but on the precision of the estimation of the primary endpoints and the ratios between various ALC subgroups.

For example, the Phase 2 and 3 controlled and uncontrolled efficacy and safety studies in MS, based on data available as of May 2014 from 2470 subjects with at least 1 post-Baseline value from the interim analysis of the Integrated Summary of Safety of Tecfidera, showed that 76% of subjects had all ALC values \geq LLN and 24% had at least 1 ALC value $<$ LLN up to Week 48.

Assuming the same proportion of subjects in this study will have 1 or more ALC values $<$ LLN, it is expected that approximately 137 subjects will have all ALC values \geq LLN and approximately 43 subjects will have at least 1 ALC value $<$ LLN at Week 48, based on a total of 180 evaluable subjects at Week 48. With this sample size, the 90% CIs for the ratio of the 2 subgroups for the change from Baseline at Week 48 in lymphocyte subsets are illustrated below using the scenario of a true ratio of 0.8 (20% decrease) and 0.7 (30% decrease), respectively. When assessing lymphocyte subsets between subjects with at least 2 ALC values $<$ LLN up to the first 48 weeks of treatment versus subjects who have all ALC values \geq LLN throughout the study, the 90% CIs of the ratio would be wider, as historical data suggest that 16% of the patients treated with Tecfidera may have 2 or more ALC values $<$ LLN during the first 48 weeks of treatment.

To allow for a 10% discontinuation rate, a total of 200 subjects are planned for enrollment.

CONFIDENTIAL

The information contained herein may not be used, disclosed, or published without the written consent of
Biogen MA Inc.

Table 6: Sample Size Calculations

Primary Endpoints	SD ¹	Ratio	90% CI for the Ratio Based on N = 180	
			Subjects With At Least 1 ALC <LLN ² vs. Subjects With All ALC ≥LLN ²	Subjects With At Least 2 ALC <LLN ² vs. Subjects With All ALC ≥LLN ²
CD4 T cell count	0.32	0.8	0.73, 0.88	0.71, 0.90
		0.7	0.63, 0.77	0.63, 0.78
CD8 T cell count	0.35	0.8	0.72, 0.89	0.71, 0.91
		0.7	0.63, 0.78	0.62, 0.79
CD56 ^{bright} NK cell count	0.57	0.8	0.68, 0.95	0.65, 0.98
		0.7	0.59, 0.83	0.57, 0.86
T _{reg} count	0.95	0.8	0.60, 1.07	0.57, 1.12
		0.7	0.52, 0.93	0.50, 0.98

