5 STATISTICAL ANALYSIS METHODS

5.1 General consideration

The statistical software, SAS[®], will be used for all summaries and statistical analyses.

This study only includes a single arm. In general, statistical analyses will be descriptive in nature with appropriate measures of variation provided where applicable. For continuous endpoints, number of subjects in the analysis population, number of subjects with non-missing observations, mean, standard deviation (SD), median, minimum and maximum will be reported. For categorical endpoints, number of subjects in the analysis population, number with non-missing observations, and the percent of those with data in each category will be summarized.

Several analysis populations are defined for different analysis purposes in this study. An overview of these analysis populations will be summarized.

- Pharmacodynamic Population - it is defined as all subjects who receive at least 1 dose of study treatment and have at least 1 pharmacodynamic measurement after Baseline.

CONFIDENTIAL

The information contained herein may not be used, disclosed, or published without the written consent of Biogen Idec MA Inc.

	Protocol 109MS310 An Open-Label Study to Assess the Effects of BG00012 on Lymphocyte Subsets in Subjects With RRMS	Final Version 1.0
---	---	--------------------------

- Safety Population – it is defined as all subjects who receive at least 1 dose of study treatment.

- [REDACTED]

[REDACTED]

In general, for data that are summarized by visit, any early withdrawal, unscheduled or scheduled visits will be assigned to an appropriate scheduled visit by using a mid-point of the two visits windowing scheme. The date of first dose will be the reference point. The detailed windowing rules for lymphocyte subsets, hematology, blood chemistry and vital signs are available in [Appendix 2](#). After windowing, if there is only 1 record in the visit window, then this record will be selected; if there are multiple records falling into the same visit window with different distance from the target day then select the one closest to the target day; if there are 2 visits with the same distance from the target day, but one is before the target day and the other is after the target day, then select the later one; for laboratory test, if more than one observation falls in the same distance from the target regular scheduled visit day, the mean observation will be calculated and used in the summary statistics and analyses.

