5.3.2 Analysis of the Secondary Endpoints

The secondary endpoints are the changes from baseline in Ig isotypes (including IgA, IgM, IgG and IgG subclasses) and ALCs for up to 48 weeks. The actual values, change and percent change from baseline for Ig isotypes and ALCs at each applicable visit will be descriptively summarized. Graphical display of mean (+/- SE) of actual values and percent change from baseline over time in Ig isotypes will be presented as well. Individual patient's Ig isotypes will also be listed.

In addition, MMRM analysis will be conducted for each Ig isotype and for ALC with the change from baseline up to Week 96 as the dependent variable. The model will include visit, corresponding baseline value, age, and gender as fixed effects and an unstructured variance-covariance matrix structure. LS mean, standard error and 95% CIs will be reported for each visit.

CONFIDENTIAL

The information contained herein may not be used, disclosed, or published without the written consent of Biogen Idec MA Inc.

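### The single-arm MMRM interval for mean ALC change leaves out baseline sampling variation, so its SE is too small by about √(1−R²) for the population mean; the size depends on assumptions and the practical effect is small.

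*Protocol*

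**What the plan says.** Protocol 16.2.2.2 fits an MMRM to change from Baseline in each IgG isotype and in ALC; the model "will include visit, corresponding baseline value, age, and gender as fixed effects". That section gives no confidence level and does not mention LS means. The neighbouring primary-endpoint section, 16.2.2.1, uses 90%: "Point estimates and 2-sided 90% confidence intervals (CIs) will be derived from the model".

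SAP 5.3.2 fits the model to each Ig isotype and "for ALC with the change from baseline up to Week 96 as the dependent variable". It repeats the covariates ("The model will include visit, corresponding baseline value, age, and gender as fixed effects"), adds an unstructured covariance, and specifies the output: "LS mean, standard error and 95% CIs will be reported for each visit".

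SAP 5.1 confirms that "This study only includes a single arm", and this model has no group term. Neither document says at which baseline value the LS mean is evaluated, or whether the target is the mean change in the population or the mean at the observed baselines. On the expected effect, Protocol 5.3.2 says that "mean lymphocyte counts decreased by approximately 30% of their baseline value after 1 year".

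**The concern.** In a two-group comparison, conditioning on baseline is harmless, because the quantity of interest is a contrast between groups. Here the quantity of interest is the mean change itself. With complete data, the LS mean at the sample-mean baseline equals the ordinary mean change, but its model SE uses only the variance left after regression on baseline. The part that comes from which baselines were sampled is dropped, and a larger sample does not remove the discrepancy.

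The error is zero only if change is uncorrelated with baseline. For ALC that is unlikely on the raw scale. A fall roughly proportional to baseline produces a negative slope of change on baseline, and noise in the baseline measurement steepens it. SAP 5.3.2 names no transformation for ALC.

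The stated objective concerns the drug's effect in subjects with RRMS. Read that way, the nominal 95% interval is too narrow. The report could also show two different SEs for nearly the same mean change without explanation, because SAP 5.4.2 plots mean ± SE of change for hematology parameters, which include lymphocytes.

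**Working it through.** **The plan's own figures.** The sample size is "based on a total of 180 evaluable subjects at Week 48"; with 10% discontinuation, 180/0.90 = 200, as planned. Protocol Table 6 follows ratio × exp(±1.645 × SD × √(1/137 + 1/n₂)). For CD4, ratio 0.8, SD 0.32, n₂ = 43, this gives 0.730–0.877 against the stated 0.73–0.88. All 16 intervals agree within about 0.02 (n₂ = 43 or 29). These are between-subgroup ratios for other cell types. For ALC the plan states only the nominal 95%.

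**SE ratio.** Write change as D = a + b(B − mean B) + e.
- Variance of mean D over repeated samples: (b²Var(B) + Var(e))/n = Var(D)/n.
- Model SE² at the sample-mean baseline: Var(e)/n = Var(D)(1 − R²)/n.
- Ratio of model SE to actual SE: √(1 − R²).
- Coverage of a nominal 95% interval: 2Φ(1.96√(1 − R²)) − 1.

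R² of 0.20, 0.30 and 0.37 gives coverage of 92%, 90% and 88%.

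**Range of R² (assumptions).** Let ρ be the correlation of baseline with follow-up ALC, and s the ratio of follow-up SD to baseline SD. Then R² = (ρs − 1)² / (s² + 1 − 2ρs).

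| s | R² for ρ from 0.9 to 0.4 | Coverage |
|---|---|---|
| 1.0 | 0.05 to 0.30 | 94.4% to 89.9% |
| 0.9 | 0.19 to 0.38 | 92.2% to 87.9% |
| 0.8 | 0.36 to 0.46 | 88.3% to 84.9% |
| 0.7 | 0.51 to 0.60 | 83.0% to 78.8% |

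In the last two rows coverage does not move steadily with ρ, so the extremes over ρ are shown. The row s = 0.7 is the case where the SD shrinks in proportion to a 30% fall. Example: s = 0.7, ρ = 0.9 gives R² = (0.63 − 1)²/(0.49 + 1 − 1.26) = 0.1369/0.23 = 0.595, SE ratio 0.636, coverage 78.8%.

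**Simulation of the planned model.** Ten ALC visits, one common baseline slope, unstructured covariance, age, gender at the observed share, complete data, n = 180, 1,500 runs per scenario.
- SD constant on treatment: coverage 93–95% at Week 4 and 90.5–93.5% at Week 48.
- SD shrinking with a 30% fall: 92–96% at Week 4 and 79–84% at Week 48.
- Unconditional interval (SD of change/√n): 94–96% throughout.

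The shortfall differs by visit because a single baseline slope serves all visits.

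**Log scale.** A uniform proportional fall leaves the log SD unchanged, so the s = 1.0 row applies: about 90–95%. If only measurement noise (SD w) links change to baseline, R² = w⁴/(Var(B)Var(D)). Assume w = 0.18, total baseline log-SD 0.25 and total log-change SD 0.32. Then R² = 0.00105/(0.0625 × 0.1024) = 0.164 and coverage is 92.7%. With w = 0.12, 0.40 and 0.32, R² = 0.013 and coverage is 94.9%.

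**Ig isotypes.** With ρ = 0.9 and s = 1, the SE ratio is 0.975, so the SE is 2.5% too small.

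**Absolute size.** Assume lognormal ALC with median 1.9 × 10⁹/L and a 30% fall. With SD of change 0.60 and R² 0.24, the half-width is 1.96 × 0.60/√180 = 0.088 unconditionally and 0.088 × √0.76 = 0.076 from the model. Across baseline log-SD 0.25–0.40, log-change SD 0.25–0.32 and noise 0.12–0.18, the gap stays below about 0.02 × 10⁹/L, against a mean change of about −0.52 to −0.59.

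**The case against.** The strongest reply is that baseline-adjusted MMRM is conventional and its interval is correct for the mean change at the observed baselines. Neither document names the unconditional mean as the target. That stands: a reader might infer that the interval is simply invalid, and it is not. The fault is the mismatch between a conditional SE and a result that will naturally be read as the mean change in RRMS.

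Second, a reader might infer that this interval is the only information on precision, or the whole inferential result. The documents do not support that. SAP 5.1 and 5.3.2 plan the raw mean and SD of ALC change, from which an unconditional interval can be formed. SAP 5.4.2 plans the mean ± SE plot, in the safety rather than the pharmacodynamic population. Although Protocol 16.2.2 plans no hypothesis tests, SAP 5.3.1 plans Wilcoxon signed rank tests for lymphocyte subsets, and the TBNK list in SAP Appendix 1 includes absolute lymphocytes. The subset MMRM does give 95% CIs, but by ALC subgroup. The model in SAP 5.3.2 still gives the only planned 95% CI for the overall ALC change.

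Third, the analysis might be run on the log scale. Protocol 16.2.2.2 calls for the same type of MMRM as the primary analysis, and 16.2.2.1 allows transformation. SAP 5.3.2 does not repeat this for ALC, so the scale is open. On the log scale most of the problem goes.

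**Conclusion.** The point holds. With the default LS mean, the planned SE for overall ALC change omits baseline sampling variation and is too small by about √(1−R²) for the population mean, and nothing in the plan corrects this.

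Its size cannot be derived from the documents. A reader might want a single coverage figure such as 88–92%. That needs a correlation of change with baseline of about 0.45–0.61 in absolute value (R² 0.20–0.37), which neither document gives. It is one part of a raw-scale range of about 79–95% at Week 48. These figures assume complete data and gender at its observed share. Equal gender weights with an assumed 2:1 mix would raise coverage by about one point or less in most cases.

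This is a wrong error bar on a descriptive secondary endpoint. It does not change how a fall near 30% would be read, so the priority is low.

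**What to change.** In SAP 5.3.2 and Protocol 16.2.2.2:
- State that the target is the mean change in the RRMS population.
- Make the response the ALC (or Ig) value at Baseline and at each visit, with visit as a fixed effect, unstructured covariance, and age and gender main effects if wanted.
- Report visit-minus-Baseline contrasts with SE and 95% CI.

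With complete data this reproduces the raw mean change and SD/√n. With missing visits, Baseline still contributes under the same missing-at-random assumption.

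Alternatively, keep the stated model and take the CI from a subject-level bootstrap, refitting and recomputing the LS mean at each resample's own mean baseline.

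The cost is SAP wording and a few lines of code. For ALC the covariance matrix grows from 10 to 11 time points (55 to 66 parameters). ALC intervals widen by 1/√(1−R²) − 1: about 3% at R² = 0.05, 20% at 0.30, and 57% at the extreme of 0.595. In absolute terms this remains modest.
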